2.12 Biomarkers

[figure not shown]
Not applicable.

[figure not shown]

[figure not shown]

2.14 Interim analysis

An interim analysis on the efficacy and safety data has been performed after all patients have completed the Treatment Period 1 (Week 24 visit), and will be performed after all patients have completed the Treatment Period 2 (Week 52 visit), in order to support regulatory filing. Additional analyses may be performed to support Health Authority interactions, as necessary.

3 Sample size calculation

With a very low prevalence of AS in Japan (0.0065%), it is expected that approximately 30 patients will be enrolled in this study based on the feasibility assessment. With 30 patients and assuming an ASAS20 response rate of 60% at week 16 (F2310), the estimated lower limit of 95% confidence interval for the ASAS20 response rate in Japanese population treated with secukinumab 150 mg s.c. will be approximately 42.5%, which is well above the upper limit of the 95% confidence interval for the response rate of control group derived in F2310 (ASAS20 response: 28.4%, Confidential Interval: 18.1-38.7).

4 Change to protocol specified analyses

There is no change.

5 Appendix

5.1 Imputation rules

5.1.1 Study drug

In case of missing date of study treatment, the date of the visit in which the missing date occurs will be imputed.

5.1.2 AE date imputation

The following table explains the notation used in the logic matrix. Please note that missing start dates will not be imputed.

Note, it may happen that the imputed AE start is after AE end date.

Table 5-1 Convention for imputation rule for AE start date

	Day	Month	Year
Partial adverse event start date	Not used	MON	YYYY
Treatment start date (TRTSDT)	Not used	TRTM	TRTY

The following matrix explains the logic behind the imputation.

Table 5-2 Imputation algorithm for AE start date

	MON missing	MON < TRTM	MON = TRTM	MON > TRTM
YYYY missing			NA	
YYYY < TRTY	01JULYYYY		15MONYYYY	
YYYY = TRTY	TRTSDT + 1	15MONYYYY	TRTSDT + 1	01MONYYYY
YYYY > TRTY	01JANYYYY		01MONYYYY	

AE end date will not be imputed.

5.1.3 Concomitant medication date imputation

The following table explains the notation used in the logic matrix for the partial start date of the concomitant medication (CMD). Please note that missing start dates will not be imputed.

Note, it may happen that the imputed CMD start date is after CMD end date.

Table 5-3 Convention for imputation rule for concomitant medication start date

	Day	Month	Year
Partial concomitant medication (CMD) Start Date	Not used	MON	YYYY
Treatment Start Date (TRTSDT)	Not used	TRTM	TRTY

The following matrix explains the logic behind the imputation.

Table 5-4 Imputation algorithm for concomitant medication start date

	MON missing	MON < TRTM	MON = TRTM	MON > TRTM
YYYY missing	NA			
YYYY < TRTY	01JULYYYY	15MONYYYY		
YYYY = TRTY	*	15MONYYYY	*	01MONYYYY
YYYY > TRTY	01JANYYYY	01MONYYYY		

* if CRF pages specify the date is prior to TRTSDT, then TRTSDT -1: otherwise TRTSDT + 1.

Concomitant medication end date will not be imputed.

5.2 AEs coding/grading

Please see section 2.8.1.

5.3 Laboratory parameters derivations

Normal ranges for differential count of leukocytes (absolute value) will be as follows:

Table 5-5 Normal ranges for differential counts of leukocytes

Laboratory test name	(Low, High) (Unit)
Basophils (absolute)	(0.0, 0.2) (x 10E3/uL)
Eosinophils (absolute)	(0.0, 0.7) (x 10E3/uL)
Lymphocytes (absolute)	(1.0, 4.0) (x 10E3/uL)
Monocytes (absolute)	(0.1, 0.9) (x 10E3/uL)
Neutrophils (absolute)	(1.6, 7.4) (x 10E3/uL)

5.4 Statistical models

5.4.1 Primary analysis

Summary statistics for binary and categorical data

Summary statistics for discrete variables will be presented in contingency tables and will include count and frequency in each category. If applicable, confidence intervals will be derived as well based on the score method including continuity correction (Newcombe, 1998):

With z as $(1 - \alpha/2)$ -quantile of the standard normal distribution (SAS: $z = \text{PROBIT}(1 - \alpha/2)$), n as total number of patients (i.e. number of patients in the denominator), and p as estimated crude incidence (number of patients with event / n) it is $q = 1 - p$

Then the lower limit is

$$L = 100 \times \max \left(0, \frac{2np + z^2 - 1 - z\sqrt{z^2 - 2 - \frac{1}{n} + 4p(nq + 1)}}{2(n + z^2)} \right)$$

and the upper limit is

$$U = 100 \times \min \left(1, \frac{2np + z^2 + 1 + z\sqrt{z^2 + 2 - \frac{1}{n} + 4p(nq-1)}}{2(n+z^2)} \right).$$

In addition, if $L > p$ then $L = p$ and if $U < p$ then $U = p$.

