2.1 Data analysis general information

The data will be analyzed by Novartis. SAS (version 9.4 or later) in GPSII will be used for all analyses in this SAP.

Summary statistics for continuous variables will include the number of patients (N), mean, standard deviation, minimum, median, maximum (lower quartile, upper quartile, if appropriate). Summary statistics for discrete variables will be presented in contingency tables and will include absolute and relative frequencies. The 95% confidence interval will be provided for efficacy variables as appropriate.

The cut-off date of the interim analysis at the applicable Week (e.g., Week 52) will be defined as the date of the last patient visit at the Week. All available data up to the cut-off date will be used in the interim analysis. The analysis results for efficacy variables by week will be presented only up to the applicable week (e.g., in case the Week 52 interim analysis, efficacy results at Week 60 will NOT be presented), while all available results from safety variables will be presented.

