2.8.1 Adverse events (AEs)

Only treatment emergent adverse events are summarized. However all AEs are included in the listing with flags for treatment emergent. Non-treatment emergent adverse events may be summarized separately upon request.

Treatment emergent adverse events are defined as events started after the first dose of study medication or events present prior to the first dose of study medication but increased in severity after dosing based on preferred term and within last dose + 84 days.

The crude incidence of treatment emergent adverse events will be summarized by primary system organ class and preferred term. Confidence intervals for the crude rate will be derived as described in 5.4.4. In addition, exposure time-adjusted rates (incidence rate) including 95% confidence intervals will be provided for entire treatment period described below.

- Primary SOC level for AE
- Primary SOC and PT level for SAE

- Level 1 for risks and SMQ

AEs will be summarized by presenting the number and percentage of patients having any AE, having an AE in each primary system organ class and having each individual AE (preferred term). AEs reported will be presented in descending frequency according to its incidence in all patients starting from the most common event. Summaries (crude incidences only) will also be presented for AEs by severity and for study treatment related AEs. If a particular AE 'severity' is missing, this variable will be listed as missing and treated as missing in summaries. If a patient reported more than one adverse event with the same preferred term, the adverse event with the greatest severity will be presented. If a patient reported more than one adverse event within the same primary system organ class, the patient will be counted only once with the greatest severity at the system organ class level, where applicable.

Separate summaries will be presented for AEs possibly related to study treatment, death, serious adverse events (SAEs), SAEs possibly related to study treatment, AEs leading to discontinuation and AEs leading to temporary dose interruption.

Adverse events will also be reported separately by SMQ according to MedDRA, using a narrow search. The MedDRA version used for reporting the study will be described in a footnote.

In addition, crude incidence of AEs will be derived by 3 months intervals (only the first occurrence will be counted in case of multiple occurrences.)

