5.4.3 Secondary analysis

See Section 5.4.1 Primary analysis.

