5.4.4 Safety analysis

Crude incidence and related risk estimates

Crude incidence and $100*(1 - \alpha)\%$ confidence interval

For n patients, each at risk to experience a certain event with probability π , the crude incidence is estimated as $p = x/n$, where x is the number of patients with the event.

Absolute and relative frequencies will be displayed as well as 95% confidence interval for the relative frequency based on the score method including continuity correction ([Newcombe 1998](#)) as Section 5.4.1.

If appropriate, an exact $100*(1 - \alpha)\%$ confidence interval ([Clopper-Pearson 1934](#)) will be obtained by using the SAS procedure PROC FREQ with the EXACT BINOMIAL statement. However, the confidence interval derived via the score method including continuity correction will be the default in safety analyses.

Exposure adjusted incidence rate and $100*(1 - \alpha)\%$ confidence interval

It will be assumed that for each of n patients in a clinical trial the time t_j ($j = 1, \dots, n$) to the first occurrence of a certain treatment emergent event is observed, or if the event was not experienced, the (censored) time to the end of the treatment period or last dose plus 84 days whichever occur earlier. The sequence of first occurrences of an event will be modeled to follow approximately a Poisson process with constant intensity θ . The rate parameter θ will be estimated as $\lambda = D/T$, where $T = \sum_{j=1}^n t_j$ and D is the number of patients with at least one event.

Conditionally on T , an exact $100*(1 - \alpha)\%$ confidence interval for a Poisson variable with parameter θT and observed value D can be obtained based on ([Garwood, 1936](#)), from which an exact $100*(1 - \alpha)\%$ confidence interval for D/T will be derived as follows ([Sahai, 1993](#); [Ulm, 1990](#)):

Lower confidence limit: $L = \frac{0.5c_{\alpha/2,2D}}{T}$ for $D > 0$, 0 otherwise,

Upper confidence limit: $U = \frac{0.5c_{1-\alpha/2,2D+2}}{T}$

where $c_{\alpha,k}$ is the α th quantile of the Chi-square distribution with k degrees of freedom.

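### SAP 5.4.1 truncates confidence limits expressed in percent against a rate expressed as a proportion, so the rule as written overwrites the lower limit of every nonzero rate

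*SAP*

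**What the plan says.** SAP 5.4.1 prints both limits of the score interval with continuity correction. Each begins with a factor of 100, and the bounds at 0 and 1 sit inside that factor, so L and U are percentages. The rate is defined differently: "p as estimated crude incidence (number of patients with event / n) it is $q = 1 - p". It is therefore a proportion between 0 and 1, and 5.4.4 again uses x/n. The section closes with "In addition, if $L > p$ then $L = p$ and if $U < p$ then $U = p".

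The formula reaches beyond the primary endpoint:

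- SAP 5.4.3 (secondary analysis) consists of "See Section 5.4.1 Primary analysis".
- SAP 5.4.4 states that "the confidence interval derived via the score method including continuity correction will be the default in safety analyses".
- SAP 2.8.1 makes the safety use a firm commitment: "Confidence intervals for the crude rate will be derived as described in 5.4.4".
- For efficacy the commitment is conditional. SAP 2.1 says "The 95% confidence interval will be provided for efficacy variables as appropriate", and 5.4.1 attaches a similar condition.

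**The concern.** The closing rule compares and substitutes quantities on two scales. Nothing in 5.4.1, 5.4.3 or 5.4.4 redefines p as a percentage, and it could not be one inside the formulas, where q is 1 minus p. Taken at its word, the lower half of the rule acts where it should not and the upper half fails to act where it should.

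The study tests no hypothesis (SAP 2.5.2 and 2.7.2), so estimates and any intervals around them carry the statistical content. SAP 2.14 ties the analyses to regulatory filing. A wrong lower limit on a common event would stand out, but on a rare one it need not. At one decimal, 1/30 would show 0.0 instead of 0.2, and a safety table by preferred term may hold many such rows.

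**Working it through.** **Inputs.** n = 30 (SAP section 3); two-sided 95% level (SAP 2.1), so z = 1.95996 and z² = 3.8415; L, U, p and the truncation rule from SAP 5.4.1.

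**The plan's own figure.** SAP section 3 gives a lower limit of about 42.5% for a 60% response in 30 patients. The simple normal-approximation limit reproduces it: 0.6 − 1.96 × sqrt(0.6 × 0.4 / 30) = 0.4247. That figure does not use the 5.4.1 formula, which gives 40.75% for 18/30, and it is not affected by this point.

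**Formulas before truncation.**

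L = 100 × [2np + z² − 1 − z × sqrt(z² − 2 − 1/n + 4p(nq + 1))] / [2(n + z²)]

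U = 100 × [2np + z² + 1 + z × sqrt(z² + 2 − 1/n + 4p(nq − 1))] / [2(n + z²)]

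At n = 30 the denominator is 2 × 33.8415 = 67.683.

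**18/30 (p = 0.6), lower.** Root: sqrt(3.8415 − 2 − 0.0333 + 2.4 × 13) = sqrt(33.008) = 5.745. L = 100 × (36 + 3.8415 − 1 − 1.95996 × 5.745) / 67.683 = 40.75. Literal rule: 40.75 > 0.6, so L becomes 0.60. On a common scale, 40.75 < 60 and L stands.

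**1/30 (p = 0.0333), lower.** Root: sqrt(1.8081 + 0.1333 × 30) = sqrt(5.8081) = 2.410. L = 100 × (2 + 3.8415 − 1 − 1.95996 × 2.410) / 67.683 = 0.17. Literal rule: 0.17 > 0.033, so L becomes 0.03. On a common scale, 0.17 < 3.33 and L stands.

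**30/30 (p = 1), upper.** Root: sqrt(3.8415 + 2 − 0.0333 − 4) = sqrt(1.8081) = 1.3447. U = 100 × (60 + 3.8415 + 1 + 1.95996 × 1.3447) / 67.683 = 99.70. Literal rule: 99.70 is not below 1, so nothing happens and U lies under the 100% estimate. On a common scale, 99.70 < 100 and U is set to 100.

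**0/30, lower.** The formula gives 0.30. Because p = 0 on either scale, both readings set it to 0.

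| Count | Estimate (%) | Limits, common scale | Limits, literal rule |
|---|---|---|---|
| 0/30 | 0 | 0 to 14.13 | 0 to 14.13 |
| 1/30 | 3.33 | 0.17 to 19.05 | 0.03 to 19.05 |
| 2/30 | 6.67 | 1.16 to 23.51 | 0.07 to 23.51 |
| 18/30 | 60 | 40.75 to 76.78 | 0.60 to 76.78 |
| 30/30 | 100 | 85.87 to 100 | 1.00 to 99.70 |

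**All counts.** At n = 30 the two readings differ in the lower limit for 30 of 31 counts and in the upper limit for 1 of 31. Over every n from 1 to 300 and x from 1 to n (300 × 301 / 2 = 45,150 cases), L exceeds p in all 45,150 and U is below p in none. With the comparison made against 100p, the rule acts only at x = 0 (lower) and x = n (upper), once each per n.

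**Smaller denominators.** The upper shortfall at x = n grows as n falls: the untruncated U is 99.08 at n = 10 and 98.13 at n = 5. This would matter if intervals are produced for small subgroups under SAP 2.2.1.

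**The case against.** The strongest reply is that this is a notation slip with only one sensible reading. Truncation at the estimate can only mean that the interval must contain it, the method is named and referenced, and both formulas are printed in full. The documents contain no code or output, and SAP 2.14 reports that "An interim analysis on the efficacy and safety data has been performed after all patients have completed the Treatment Period 1", so a working program may already exist. A program that followed the text literally would also expose itself, because no nonzero rate could have a lower limit above 1. An illustrative 24/30 in the top row of an adverse-event table would show 80% with a lower limit of 0.8 instead of 60.9. In the row that looks plausible, 1/30, the error is only 0.14 percentage points. Efficacy intervals are conditional, and no decision depends on them.

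Most of this stands. The intent is clear, no reported number is shown to be wrong, and the count of 30 in 31 describes how the printed rule behaves, not how likely a wrong table is. It does not make the text correct. An independent programmer should be able to reproduce a written formula as it stands, and this one gives wrong limits when followed. It is also the default for the adverse-event intervals that the SAP commits to producing.

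**Conclusion.** The point holds. SAP 5.4.1 mixes percentages and a proportion in its truncation rule, and nothing elsewhere in the documents repairs it. Read literally at n = 30, the lower limit is too low for every nonzero count, by 40.15 points at 18/30 (40.75 − 0.60) and 0.14 points at 1/30. The upper limit at 30/30 is 0.3 points too low and leaves the estimate outside its own interval.

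This rests on the formula as printed, a 95% level and 30 patients in the denominator; the pattern is the same at every n checked. Whether any produced table is affected depends on a program that is not available here. The text should be corrected and the program checked before the Week 52 analysis, which this SAP still lists as to come.

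**What to change.** Replace the last sentence of SAP 5.4.1 with: if L > 100p then L = 100p, and if U < 100p then U = 100p. Equivalently, truncate on the proportion scale and multiply by 100 afterwards. Sections 5.4.3 and 5.4.4 refer back to 5.4.1 and need no change of their own.

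Then run the program behind the Week 24 output at three counts with n = 30:

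- 0/30 should give 0 to 14.13.
- 18/30 should give 40.75 to 76.78.
- 30/30 should give 85.87 to 100.

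If all three agree, only the text was wrong. If not, the Week 24 intervals that used the formula need to be rerun. The certain cost is one line of SAP text and a three-value check; data, design and hypotheses are unaffected.

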5.4.2 Key secondary analysis

Not applicable.

5.4.3 Secondary analysis

See Section 5.4.1 Primary analysis.

5.4.4 Safety analysis

Crude incidence and related risk estimates

Crude incidence and $100*(1 - \alpha)\%$ confidence interval

For n patients, each at risk to experience a certain event with probability π , the crude incidence is estimated as $p = x/n$, where x is the number of patients with the event.

Absolute and relative frequencies will be displayed as well as 95% confidence interval for the relative frequency based on the score method including continuity correction ([Newcombe 1998](#)) as Section 5.4.1.

If appropriate, an exact $100*(1 - \alpha)\%$ confidence interval ([Clopper-Pearson 1934](#)) will be obtained by using the SAS procedure PROC FREQ with the EXACT BINOMIAL statement. However, the confidence interval derived via the score method including continuity correction will be the default in safety analyses.

Exposure adjusted incidence rate and $100*(1 - \alpha)\%$ confidence interval

It will be assumed that for each of n patients in a clinical trial the time t_j ($j = 1, \dots, n$) to the first occurrence of a certain treatment emergent event is observed, or if the event was not experienced, the (censored) time to the end of the treatment period or last dose plus 84 days whichever occur earlier. The sequence of first occurrences of an event will be modeled to follow approximately a Poisson process with constant intensity θ . The rate parameter θ will be estimated as $\lambda = D/T$, where $T = \sum_{j=1}^n t_j$ and D is the number of patients with at least one event.

Conditionally on T , an exact $100*(1 - \alpha)\%$ confidence interval for a Poisson variable with parameter θT and observed value D can be obtained based on ([Garwood, 1936](#)), from which an exact $100*(1 - \alpha)\%$ confidence interval for D/T will be derived as follows ([Sahai, 1993](#); [Ulm, 1990](#)):

Lower confidence limit: $L = \frac{0.5c_{\alpha/2,2D}}{T}$ for $D > 0$, 0 otherwise,

Upper confidence limit: $U = \frac{0.5c_{1-\alpha/2,2D+2}}{T}$

where $c_{\alpha,k}$ is the α th quantile of the Chi-square distribution with k degrees of freedom.

